#### 9.2.7. Volume of blood to be drawn from each patient

The total volume of blood that will be drawn from each patient in this study will vary depending on how long the patient remains on study. Table 9-4 indicates the range for patients during the treatment period (28 months).

Table 9-4 Volume of blood to be drawn from each patient during the screening and treatment period (Screening to End of study visit)

Assessment	Max volume (1 draw)	No. of samples (30 days)	Max volume (30 days)	No. of samples (Total)	Max volume (Total)
On site laboratory analyses					
Biochemistry	4 mL	Max 7	28 ml	Max 23	92 mL
Haematology	4 mL	Max 7	28 mL	Max 23	92 mL
Serum virology & pregnancy test (screening)	4.5 mL	Max 1	4.5 mL	Max 1	4.5 mL
Immunoglobulin levels	5 mL	Max 2	10 mL	Max 5	25 mL
Coagulation	4 mL	Max 1	4 mL	Max 2	8 mL
HAMA at screening	4 mL	Max 1	4 mL	Max 1	4 mL
Immunogenicity assessment  (lilotomab, Betalutin ADA)	6 mL	Max 2	12 mL	Max 7	42 mL
RTX immunogenicity (ADA)/PK 	4 mL	Max 2	8 mL	Max 7	28 mL
Minimal Residual Disease	8 mL	Max 1	8 mL	Max 5	40 mL
Pharmacokinetic – Total radioactivity 	2 mL	Max 8	16 mL	Max 8	16 mL
HLA haplotyping (optional)	2 mL	Max 1	2 mL	Max 1	2 mL
In vitro T-cell responses  (optional)	100 mL	Max 1	100 mL	Max 3	300 mL
TOTAL - maximum volume to be drawn for patients not participating in the PK  and in vitro T-cell assessments	45.5 mL	-	108.5 mL	-	337.5 mL
TOTAL - maximum volume for a few patients (<10) participating in the PK  but not in vitro T-cell assessments	47.5 mL	-	124.5 mL	-	353.5 mL
TOTAL - maximum volume to be drawn for patients participating in the in vitro T-cell but not PK  assessments	145.5 mL	-	208.5 mL	-	637.5 mL
TOTAL - maximum volume to be drawn for patients participating in both the PK  and in vitro T-cell assessments	147.5 mL	-	224.5 mL	-	653.5 mL

Max = maximum number of samples to be taken from screening to End of Study

<sup>2 Monitoring of rituximab concentration in serum and the ADA response towards rituximab.

<sup>3 To be performed at Radium Hospital (Oslo, Norway) only; otherwise optional

<sup>4At Radium Hospital (Oslo, Norway) only. Optional, additional blood volumes collected to explore the anti-tumour T cell responses

#### 9.2.8. Pregnancy

• Details of all pregnancies in female patients and female partners of male patients will be collected after the start of study treatment. The pregnant patient or the patient's partner should be followed-up during the entire course of the pregnancy up to 6-8 weeks beyond the estimated delivery date.

- If a pregnancy is reported, the Investigator should inform the Sponsor within 24 hours of learning of the pregnancy and should follow the procedures outlined in Appendix 3.
- Abnormal pregnancy outcomes (e.g. spontaneous abortion, foetal death, stillbirth, congenital anomalies or ectopic pregnancy) are considered SAEs.

#### 9.3. Pharmacokinetics

#### 9.3.1. Assessments

Betalutin PK samples will be collected from patients to evaluate whether the combination with RTX impact the total radioactivity in blood profile observed in the LYMRIT 37-01 study. *In vitro* measurements will be performed by measuring the total radioactivity (Betalutin, Lu-satetraxetan chelate, Lu-DTPA chelate, and Lu) per mL of blood using a gamma counter. This assessment will be mandatory at Radium Hospital (Oslo, Norway), otherwise optional.

It has to be noted that it is not expected to detect Lu in blood due to its high binding affinity to satetraxetan and DTPA. DTPA chelates the Lu not radiolabelled to satetraxetan in Betalutin formulation, with Lu-DTPA chelate expected to have a fast-renal clearance [44-46].

RTX is widely used in onco-haematology at a dose of 375 mg/m^2, as neither dose-response relationship nor DLT were identified. As PK studies have demonstrated large inter-individual variability of rituximab exposure [47, 48], monitoring of RTX serum concentration will be performed to support the assessment of any potential interference of RTX in immunogenicity assessments (see Section 9.2.6.5).

#### **9.3.2.** Human biosamples collection schedule

Sampling of peripheral blood for Betalutin PK will be performed at the following approximate time points:

- Before lilotomab administration (baseline)
- After Betalutin administration:
- 5 ( $\pm$ 2), and 60 ( $\pm$ 10) minutes
- 2 hours ( $\pm 15$  minutes), 24 ( $\pm 4$ ) hours, and 96 ( $\pm 24$ ) hours
- 7 ( $\pm$ 2) days and 28 ( $\pm$ 2) days

It has to be noted that on Days 7 and 28, PK sampling should be done before RTX dosing. The time points mentioned are approximate time points. The exact time point when the sample is taken needs to be recorded in the eCRF. Each patient group will be monitored continuously, and adaptation of the sampling times may become necessary depending on the results.

Sampling of peripheral blood for RTX concentration in serum will be performed at the time points agreed for the immunogenicity assessments (See Section 9.2.6.5.2.).

#### 9.3.3. Human biosamples handling

#### 9.3.3.1. Total radioactivity in blood

A volume of approximately 2 mL of peripheral blood will be collected on EDTA at each time point (see above and Section 1-2). An exact volume of 1 mL of peripheral blood will be transferred on-site into a 5 mL transfer tube. Radioactivity measurement will be performed on-site at Nordic Nanovector ASA (Oslo, Norway) or selected sites that are experienced and equipped to perform these assessments. The total radioactivity per mL of blood will be determined from each sample.

Instructions for handling procedures, preparation, storage and shipping of the serum samples will be provided in the laboratory manual for this study.

## 9.3.3.2. Monitoring of RTX concentration in serum

A volume of approximately 4 mL of peripheral blood will be collected and handled as described in Section 9.2.6.5. and Section 1-2.

Serum samples will be shipped to Covance Central Laboratories (Geneva, Switzerland), where they will be biobanked for future use.

Instructions for handling procedures, preparation, storage and shipping of the serum samples will be provided in the laboratory manual for this study.

## 9.4. Biodistribution and dosimetry

The biodistribution and dosimetry study will provide estimates for the absorbed radiation dose to normal body structures as well as to tumours that can be identified in the images. The radioactivity in the actual organs will be measured in absolute terms, at different times after injection. The time series will allow to estimate the cumulative activity in each organ and by measurements/estimates of organ weight the absorbed dose.

Measurements will be performed as described in Appendix 5.

The measurements will be performed on a SPECT/CT scanner containing 2 gamma camera heads (Siemens SYMBIA –T16) equipped with medium energy collimators, which. will be used for CT, SPECT, and whole-body scanning. Quantification will be carried out by use of the software of the vendor and using computer programs (IDL, ITT visual solutions) Full details of the scans required for biodistribution and dosimetry and of acquisition specifications are provided in a dedicated dosimetry protocol.

The images obtained will enable the characterisation of the biodynamics and the calculation of the cumulative activity in each organ, with dose estimates obtained using the OLINDA program.

The conjugated whole-body studies and the quantification in regions drawn around each organ together with assay of activity in blood will allow for:

- Estimation of whole-body retention of radioactivity at set imaging times post-injection.
- Estimation of the individual organ uptake/retention of radioactivity at set points after injection.
- Estimate retention of administered radioactivity in blood.
- Calculation of estimated absorbed radiation dose to target organs and to tumours.

#### 9.5. Biomarkers

Biomarker research is part of this study. Following informed consent from the patients, human biosamples, including but not exclusive to tumour tissue biopsy, needle aspirate and peripheral blood samples, will be collected to evaluate pharmacodynamics [49, 50] and gene expression changes related to disease treatment and/or relapse/disease progression in tumour [51-56]. HLA class I and II haplotype of the patients will be addressed using DNA extracted from either peripheral blood leucocytes or saliva [43, 57]. Anti-tumour T-cell responses will be measured by flow cytometry after co-culture of peripheral blood mononuclear cells and autologous lymphoma cells [58] and other relevant in vitro biomarker analyses.

Details regarding the assessments, technologies in scope and biobanking are reported in Table 9-5. Except for CD37/CD20 expression in tumour prior to treatment and monitoring of the MRD, these assessments are optional, and some will be performed at selected sites only (e.g. anti-tumour T-cell responses). The results of these analyses are not required for enrolment into the study and may not be reported to the clinical study database, nor have impact on patient management but could be published in scientific journals.

Instructions for handling procedures, preparation, storage and shipping of the biological material will be provided in the laboratory manual for this study. Analyses performed to explore the anti-tumour T-cell responses will be mainly performed at Radium Hospital (Oslo, Norway) but some analyses may require having an aliquot of this biological material (collected and biobanked at Radium Hospital (Oslo, Norway) to be sent to contract research organisations located outside of Norway.

## 9.6. Biobanking

The patient may be asked if he/she is willing to have part of the available tumour biopsy samples (archived or newly obtained at screening visit, disease progression and/or relapse) to be biobanked at Covance Central Laboratories (Geneva, Switzerland) for future analysis of the tumour tissue samples or its derivatives (DNA, RNA, proteins). If a tumour block is provided, it will be returned to the hospital upon request.

Additional biological material collected for research studies focusing the anti-tumour T-cell responses (e.g. tumour biopsy and peripheral blood samples and derivatives such as cells, plasma, DNA, RNA) collected at Radium Hospital (Oslo, Norway) only, will be processed and biobanked on-site for future use.

**Table 9-5 Biomarker assessments** 

Assessment	Human biosamples collected	Human biosamples or derivatives used in assay	Method	Schedule of assessments	Biobanking	Purpose
CD37 & CD20 expression in tumour tissue	Tumour tissue biopsy (surgical)	FFPE 5 μM slides	Immunohistochemistry, whole slide digital image quantitative analysis	Mandatory prior to treatment (archived or newly collected at screening) Optional at relapse or disease progression (newly collected biopsy)	FFPE block on-site or CCLS  5μM FFE slides to be prepared only upon sponsor request to ensure integrity of the biomaterial and quality of the analysis	To characterize PD and identify potential predictors of efficacy
Gene expression profiling in tumour	Tumour tissue biopsy (surgical) 	FFPE 5 µM slides and derivatives such as DNA, RNA and proteins	Gene expression arrays (RNA)  RNA sequencing (RNA)  DNA sequencing(DNA) Other relevant methods	Optional  Archived tumour tissue biopsies or newly collected at screening, relapse and/or disease progression	5μM FFE slides to be prepared only upon sponsor request to ensure integrity of the biomaterial and quality of the analysis	To identify prognostic and/or treatment-related predictive biomarkers
Minimal Residual Disease	Tumour tissue biopsy (surgical)  Peripheral blood	FFPE 5 μM slides  Cell and cell-free (in plasma) tumour DNA	Next generation sequencing (DNA)	Biopsy: Mandatory, archived tumour tissue biopsy or newly collected at screening  Blood: Mandatory, at prior to treatment, Week 12, Week 26, Week 52 and at EOS, unless relapse or disease progression has been clinically observed since the previous blood sample	5μM FFE slides to be prepared only upon sponsor request to ensure integrity of the biomaterial and quality of the analysis 5μM FFE slides to be prepared only upon sponsor request to ensure integrity of the biomaterial and quality of the analysis  Bulk material (whole blood without plasma) and plasma, at CCLS	To calibrate the blood MRD test  To assess early treatment response and detect relapse

Assessment	Human biosamples collected	Human biosamples or derivatives used in assay	Method	Schedule of assessments	Biobanking	Purpose
In vitro anti- tumour T-cell response	Peripheral blood and tumour tissue biopsy (surgical or needle aspirate – See Tables  1-1 and 1-2)	Peripheral blood leucocytes, tumour cells, plasma, and derivatives such as DNA, RNA and proteins	In vitro cell based assay using flow cytometry as readout and other biomarker analyses (DNA, RNA, proteins)	Optional Peripheral blood: Prior to treatment, Week 12 and Week 39 Tumour biopsy: Prior to treatment, Day -1 or Day 0, Week 12 and Week 25	Peripheral blood leucocytes, tumour cells, plasma and derivatives such as DNA, RNA, proteins, at Radium Hospital (Oslo, Norway)	To explore further the anti- tumour T-cell responses driven by the combination of lilotomab, Betalutin and RTX
HLA class I II haplotype	Peripheral blood Saliva sample or mouth swab is acceptable if blood collection not possible	DNA	Gene array (DNA)	Optional Prior to treatment	Peripheral blood, saliva, mouth swab and at CCLS	To (i) investigate the mechanism underlying a potential ADA response and (ii) characterize the antitumour T-cell response

<sup>1**NOTE:** No additional tumour tissue biopsy will be collected (sample may be taken from an archived and/or newly collected biopsy at screening, relapse and/or disease progression for CD20 & CD37 expression in tumour)

#### 10. Statistical Considerations

## **10.1.** Statistical Analyses

The study is a single-arm, open-label study to further assess the risk/benefit of a pre-dose of lilotomab and Betalutin to enhance tumour response to RTX therapy. Six to 12 patients is a reasonable sample size to evaluate any potential safety/tolerability signals and for obtaining preliminary estimates of the response rates and variability of the response rates.

The primary endpoint is the frequency and type of AEs. Study data will be summarised with respect to demographic and baseline characteristics, safety observations and measurements, efficacy observations and measurements (response rates, duration of response, PFS, TTP, OS), and PK measurements. Categorical data will be presented in tables; descriptive statistics will be used to summarise response rates, etc. Patients who have withdrawn from the study, including those who have died, will be counted as having PD for all visits after the time of withdrawal.

The number and percentage of patients with each response, and overall (CR + PR) will be presented for each time point for the ITT population. All data obtained after treatment with lilotomab/Betalutin will be summarized by the dose of Betalutin received and overall doses.

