#### **Secondary**

- Responses (overall response rate [ORR], CR, PR, stable disease [SD], progressive disease [PD]) as per Cheson 2014
- Duration of response (DoR)
- Progression free survival (PFS)
- Time to progression (TTP)
- Overall survival (OS)
- Monitoring of the anti-drug antibody (ADA) response towards lilotomab, Betalutin and/or RTX

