## 6.1. Dosing regimen

Two cohorts of 3-6 patients will initially be evaluated. The first cohort of 3 patients will be treated with a single i.v. dose of RTX (375 mg/m²) on Day -14, and then on Day 0, sequential i.v. administration of lilotomab (40 mg) followed by Betalutin (10 MBq/kg) within 4 hours on Day 0. The patients will then be administered RTX (375 mg/m²) i.v. on Days 7, 14, 21 and 28.

Patients must have received all doses of study drug and have had an adequate period of follow-up (i.e. having achieved haematological recovery to  $\leq$  grade 2) to be considered evaluable for a dose escalation decision or to determine the dose for further Phase 2 studies following enrolment of the second cohort of 3-6 patients. The dose for the next cohort of 3 patients will be determined by the Investigator(s) and Nordic Nanovector study personnel via teleconference. Decisions will be based on a review of all safety data (clinical and laboratory) and are outlined as follows:

- 1. If 0/3 patients experience a DLT (defined below), the next cohort of 3 patients will receive lilotomab 40 mg plus Betalutin 15 MBq/kg prior to RTX on Day 0.
- 2. If 1/3 patients experience a DLT, then 3 more patients will be enrolled in the current cohort at this dose level (Betalutin 10 MBq/kg).
- 3. If 2/3 patients experience a DLT, then subsequent Betalutin/lilotomab and/or RTX dosing will be determined by the Investigator(s) and Sponsor after a review of the safety data.
- 4. If 1/6 patients experience a DLT, the next cohort of 3 patients will be treated with Betalutin 15 MBq/kg.
- 5. If 0/3 patients receiving Betalutin 15 MBq/kg experience a DLT, the remainder of the patients in the study will continue to be treated with Betalutin 15 MBq/kg.
- 6. If 1/3 patients experience a DLT, then 3 more patients will be enrolled at this dose level (Betalutin 15 MBq/kg).
- 7. If 1/6 patients receiving Betalutin 15 MBq/kg experience a DLT, the dose for further Phase 2 studies will be Betalutin 15 MBq/kg.
- 8. If 2/6 patients experience a DLT, then 3 more patients will be treated at the lower Betalutin dose (10 MBq/kg).
- 9. The final recommendation for Betalutin/lilotomab dosing for further Phase 2 studies will be determined by the Investigator(s) and Sponsor after a review of the available safety data.

DLT is defined as:

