## 7.2. Patient Withdrawal/Discontinuation from the Study

In accordance with the Declaration of Helsinki, each patient is free to withdraw from the study at any time. Investigator(s) also have the right to withdraw patients from the study in the event of illness, AEs, or other reasons concerning the health or well-being of the patient, or in the case of lack of cooperation.

Should a patient decide to withdraw after administration of the study drug(s) or should the Investigator(s) decide to withdraw the patient, all efforts will be made to complete and report the observations up to the time of withdrawal as thoroughly as possible. A complete final evaluation at the time of the patient's withdrawal (end of study visit) should be made within 28 days (± 3 days) of receiving the last study treatment administration if ending treatment per protocol, or within 7 days of taking the decision to withdraw if it occurs > 28 days after the last study treatment administration and an explanation given of why the patient is withdrawing or being withdrawn from the study. The reason and date for withdrawal must be noted in the eCRF. If the reason for withdrawal is a clinical AE or an abnormal laboratory test result, monitoring will continue until the outcome is evident. The specific event or test result(s) must be recorded in the eCRF. If the reason for withdrawal is due to disease progression, the study site should make all effort to continue with the safety monitoring.

Haematological toxicity was observed in the phase 1/2 LYMRIT-37-01 study, with nadir values 5 to 7 weeks after injection of Betalutin. It is advisable to monitor the haematology parameters of the withdrawn patients between 6 and 9 weeks after the last RTX administration or until recovery to CTCAE grade 1 or less.

Single patient study discontinuation is per definition, when the patient:

- has completed Month 24 administration of rituximab, per protocol or
- experiences one of the following situations before per protocol end of study:
  - withdraws consent to participate in the study
  - has died
  - is lost to follow up
  - has disease progression
  - starts further anticancer therapy or
- when the patient is withdrawn for a reason other than described above

CONFIDENTIAL

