## 7.3. Replacement policy

Patients will not be replaced in the study. However, if a patient is considered to be non-evaluable for dose evaluation, enrolment of a new patient to the current cohort will be considered if there is less than the required number of evaluable patients.

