## 7.4. Lost to Follow-Up

A patient will be considered lost to follow-up if he/she repeatedly fails to return for scheduled visits and is unable to be contacted by the study site.

The following actions must be taken if a patient fails to return to the clinic for a required study visit:

- The site must attempt to contact the patient and reschedule the missed visit as soon as possible and counsel the patient on the importance of maintaining the assigned visit schedule and ascertain whether or not the patient wishes to and/or should continue in the study.
- Before a patient is deemed lost to follow-up, the Investigator or designee must make
  every effort to regain contact with the patient (where possible, 3 telephone calls and, if
  necessary, a certified letter to the patient's last known mailing address or local
  equivalent methods). These contact attempts should be documented in the patient's
  medical record.
- Should the patient continue to be unreachable, he/she will be considered to have withdrawn from the study with a primary reason of lost to follow-up.

Discontinuation of specific sites or termination of the study as a whole is discussed in Study Governance Considerations (Appendix 2).

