#### 10.1.1. Populations for analysis

Intent-to-treat (ITT) population: The ITT population will consist of all patients who were enrolled and treated with lilotomab/Betalutin, regardless if RTX therapy was initiated.

Safety Population: The safety analysis population will include all patients who received at least one dose of any study drug.

PK population: The PK population consists of all patients who have a PK assessment with a sufficient number of evaluable blood samples.

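### Section 10.1 counts every ITT patient who withdraws or dies as PD at all later visits, so each exit without recorded progression raises the by-visit, by-dose PD percentage by 1/n

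*Combined protocol and SAP*

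**What the plan says.** The synopsis lists as a secondary endpoint "Responses (overall response rate [ORR], CR, PR, stable disease [SD], progressive disease [PD]) as per Cheson 2014", and Table 3-1 repeats it. PD is thus one of four reported categories, with criteria in Table 9-1 (imaging and bone marrow findings).

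Section 10.1 plans the number and percentage of patients with each response at each time point for the ITT population. Data after lilotomab/Betalutin "will be summarized by the dose of Betalutin received and overall doses". In the same section: "Patients who have withdrawn from the study, including those who have died, will be counted as having PD for all visits" following withdrawal. The sentence gives no exception by reason for leaving and is not confined to the overall response rate.

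Section 10.1.1 defines ITT as "all patients who were enrolled and treated with lilotomab/Betalutin, regardless if RTX therapy was initiated". A patient who leaves after that point stays in the denominator.

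Exits without progression are provided for:
- Section 7.2 lists withdrawal of consent, death, loss to follow-up and start of further anticancer therapy separately from disease progression. It also lets investigators withdraw patients for "illness, AEs, or other reasons concerning the health or well-being of the patient, or in the case of lack of cooperation".
- Section 7.4 says of an unreachable patient that "he/she will be considered to have withdrawn from the study with a primary reason of lost to follow-up".
- Appendix 3 requires withdrawal for pregnancy.

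**The concern.** One label serves two purposes. In Table 9-1, PD is an observed disease state. In Section 10.1 it is also what a patient is assigned on leaving for any reason. The reason for withdrawal and the cause of death are recorded in the eCRF (Section 7.2), but the planned response table would merge them into the PD row.

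Part of the rule is needed. Progression ends both imaging and participation, so recorded PD has to be carried forward or it would disappear from later visits. The difficulty is confined to patients who leave or die with no progression recorded.

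With three to six patients per cohort, one such patient changes the PD percentage for a dose level visibly, and the table would give a reader no means of separating observed from assigned progression. Preliminary response estimates are a stated purpose of the study in Section 10.1.

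**Working it through.** **Inputs**
- Cohort size: 3 to 6 (Section 6.1). Two cohorts give 2 × 3 = 6 and 2 × 6 = 12, which reproduces the six to twelve patients in Section 10.1.
- Rule 8 of Section 6.1 can add 3 patients at 10 MBq/kg, so n there could reach 6 + 3 = 9 if six had already been treated. With six at 15 MBq/kg the total would be 15, above the stated 12, so n=9 is an upper case.
- Imaging visits: Months 3, 6, 12, 18 and 24 (Section 9.1.2).
- Exit rate: none is given in the documents.

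**Increment per exit.** Let k of n ITT patients at a dose have recorded PD, and let one other patient leave without it. The plan shows (k+1)/n. Keeping the patient in the denominator under another label shows k/n. The difference is 1/n for every k.

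| n | Rise in PD percentage (points) |
|---|---|
| 3 | 33.3 |
| 4 | 25.0 |
| 6 | 16.7 |
| 9 | 11.1 |
| 12 (all doses) | 8.3 |

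The row n=4 arises when an early leaver from a cohort of three is replaced. Section 6.1 says "Patients must have received all doses of study drug and have had an adequate period of follow-up" to be evaluable, and Section 7.3 says "enrolment of a new patient to the current cohort will be considered if there is less than the required number of evaluable patients". The replaced patient remains in ITT if lilotomab/Betalutin was given.

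**Visits affected.** An exit before Month 3 affects 5 visits. Exits in Months 3–6, 6–12, 12–18 and 18–24 affect 4, 3, 2 and 1.

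**Illustration 1 (invented, n=3).** Month 3 results are CR, SD, SD. The CR patient is then lost to follow-up and the others stay SD. The plan shows PD 1/3 (33.3%) at Months 6, 12, 18 and 24. Separate rows show PD 0/3 and not evaluable 1/3. ORR at those visits is 0/3 either way.

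**Illustration 2 (invented, n=4).** One patient withdraws consent after Betalutin but before the Day 28 rituximab and is replaced. The other three are PR, SD, SD at Month 3. The plan shows PD 1/4 (25.0%). Separate rows show PD 0/4 and not evaluable 1/4. ORR is 1/4 either way.

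**How often.** Assume patients leave without recorded PD independently with probability p. The chance of at least one such exit is 1 − (1 − p)^n.

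| p (assumed) | n=3 | n=6 |
|---|---|---|
| 5% | 14.3% | 26.5% |
| 10% | 27.1% | 46.9% |
| 20% | 48.8% | 73.8% |

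**Exits that do not count.** Patients who leave before lilotomab/Betalutin are outside ITT. Completing Month 24 is also called study discontinuation in Section 7.2, but no response imaging follows it, so it adds no assigned PD.

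**The case against.** The strongest defence is that the rule is prespecified, descriptive and conservative for response. No test or threshold is placed on PD, and in cohorts this small any one patient moves any row by 1/n. The exit reasons are on file, so the split can be recovered later, and a footnote counting the assigned PDs would prevent misreading. All of this stands, and it keeps the point minor. It does not repair the PD row, which is a planned output and would be wrong as a count of recorded progression.

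A second defence is that some exits conceal progression. That also stands: 1/n is a rise over recorded PD, not necessarily over the truth. It also limits the remedy. A reader might infer that PD should count only when the Table 9-1 criteria are met. The documents do not support that. They recognise clinically observed relapse or progression (footnote 18 to the schedule of activities, and the MRD footnotes in Section 8.2), they list disease progression as a reason for leaving (Section 7.2), and the end of study visit in Table 8-22 has no imaging. A Table 9-1-only rule would move such patients to not evaluable and understate PD by the same 1/n. Start of further anticancer therapy is a harder case, since it may reflect treatment failure; it needs to be shown by name.

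A reader might also infer that the rule sets events for DoR, PFS or TTP, because it closes the paragraph naming them. The sentence speaks of visits, and nothing in the text extends it to time-to-event endpoints.

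Finally, a SAP might restrict the rule. Section 10.1.2 and the synopsis mention one for PK, biodistribution and biomarker analyses. They do not say that it covers nothing else, so the point rests on the text available, in which no restriction appears.

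**Conclusion.** The point holds, as a minor one. Followed as written, Section 10.1 overstates recorded PD by 1/n for each ITT exit without recorded progression, at every later imaging visit: by dose 33.3 points at n=3, 16.7 at n=6 and 11.1 at n=9, and 8.3 over all doses at n=12. These figures assume the fixed ITT denominator of Section 10.1.1. How often it will happen is unknown; the probabilities shown rest on assumed exit rates.

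It would be tempting to conclude that the efficacy or dose conclusions are compromised. They are not. PD and not evaluable are both non-response, so ITT ORR and CR do not change. The primary endpoint is adverse events and laboratory changes, and dose decisions rest on dose-limiting toxicity and safety review. Toxicity leading to withdrawal remains visible in the safety summaries.

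**What to change.** Replace the sentence in Section 10.1 with:

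> PD is counted when progression is recorded by the investigator, either by the Table 9-1 criteria or as disease progression or relapse given as the reason for withdrawal or the cause of death, and is carried forward to all later visits. Other ITT patients who withdraw, start further anticancer therapy or die stay in the denominator as non-responders for ORR and CR, and are shown at later visits in separate rows (not evaluable, with the reason, including new anticancer therapy; or died without recorded progression).

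A sentence saying that this visit rule does not define DoR, PFS or TTP events would be a useful clarification, but the correction does not depend on it.

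The cost is one reworded rule and two rows in the response table. No new data are needed, because Section 7.2 already has the reason and date of withdrawal and the cause of death recorded. The downside is that some unrecorded progression will appear as not evaluable. The listed reasons keep this visible, and PD plus the two exit rows adds up to the PD row under the present rule, so a reader who prefers the conservative count can still obtain it.
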